## 17.2 Analysis Populations

**Safety Population:** The safety population (SAF) will consist of all randomized subjects who received the single dose of study drug and will be the primary population for all safety data.

**Pharmacokinetic Population:** The PK population will include all randomized subjects who received the dose of study drug and provided evaluable data that can be used for the PK analyses. The PK population will be the primary population for PK analyses.

# 17.3 Statistical Analysis of Pharmacokinetic Parameters

# 17.3.1 Primary Pharmacokinetic Endpoints

For the primary PK endpoint analyses, a linear mixed-effect model will assess the log transformed PK parameters (AUC $_{0\text{-inf}}$  and  $C_{max}$ ) of nemolizumab, with treatment (administration with AI or DCS) and injection site as fixed effects and subject as a random effect. Some clinically important baseline characteristics may also be included in the model. The AUC and  $C_{max}$  GMR between treatments (nemolizumab administered with AI [test] or DCS [reference]) after backtransformation and the corresponding 90% CI will be provided overall.

Acceptance criterion for bioequivalence is a 90% CI for the test/reference ratio of the geometric means of the parameters under consideration within the 80.00 to 125.00% range.

In addition, the GMR and 90% CI will be provided by injection site for information only.

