### 9 INVESTIGATIONAL PLAN

### 9.1 **Description of Overall Study Design and Plan**

This is a randomized, multicenter, open-label, single-dose, parallel-group study in healthy adult subjects aged 18 to 65 years to assess the relative bioavailability of a 60-mg subcutaneous dose of nemolizumab administered with AI compared to DCS, stratified by injection site. The 60-mg dose will be administered as 2 successive subcutaneous injections of 30 mg (AI or DCS).

The study duration will be up to 16 weeks and consists of an up to 28-day screening period and a 12-week PK evaluation period.

The screening period will evaluate subject eligibility. At baseline, approximately 192 subjects will be randomized 1:1 to receive 60 mg nemolizumab delivered with either AI or DCS. Subjects will be further randomized 1:1:1 to receive injection in 1 of 3 injection sites, i.e., abdomen, front upper thigh, or outer upper arm. Approximately 32 subjects in each delivery group will be assigned to each injection site.

Subjects will receive a 60-mg dose of nemolizumab via 2 subcutaneous injections of 30 mg nemolizumab. Injections should be administered at the same location (i.e., abdomen, front upper thigh, or outer upper arm) and the same side with injection sites at least 1 inch (2.5 cm) apart. Blood samples will be collected before and after nemolizumab administration for up to 12 weeks postdose for determining the complete serum PK profile of nemolizumab.

[figure not shown]
A total of 21 blood samples will be collected, i.e., 1 before and 20 after nemolizumab administration (i.e., pre-dose, 12 hours, 24 hours, 3, 4, 5, 6, 7, 8, 9, 10, 11, 15, 22, 29, 36, 43, 50, 57, 71, and 85 days post-dose). Subjects will be confined to the study center for 1 night, from nemolizumab dosing (Day 0) to the morning after nemolizumab dosing (Day 1).

Refer to Figure 2 for an overview of the study design.

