# 9.2 Discussion of Study Design

This study will assess the relative bioavailability of a 60-mg subcutaneous dose of nemolizumab administered with AI compared to DCS, stratified by injection site, including abdomen, front upper thigh, or outer upper arm. Overall, a single-dose, open-label, parallel-group PK study in healthy adult subjects is deemed appropriate for this purpose.

The parallel-group design of this study is considered necessary due to the long terminal half-life of nemolizumab ranging from 12.6 to 16.5 days and is in line with the FDA guidance "Clinical Pharmacology Data to Support a Demonstration of Biosimilarity to a Reference Product" (Guideline 2016) and the corresponding European guideline (Guideline 2014).

In accordance with the same FDA guidance, the study plans a single-dose administration, since single-dose PK studies are generally more sensitive than steady-state studies in assessing any difference in rate and extent of release of the drug substance from the drug product into the systemic circulation. Furthermore, in the case of nemolizumab, repeated-dose studies demonstrated a limited systemic accumulation over time, with median accumulation below 2, and steady-state concentrations reached after the loading dose. This confirms that the PK profile of nemolizumab is not affected by the number of administrations and can be predicted from single-dose PK parameters.

The choice of heathy adult subjects is supported by the results of the Phase 1 study CIM001JP. Study CIM001JP showed that nemolizumab concentration-time profiles in AD patients and healthy subjects shared the same shape, being described in both groups by a one-compartment distribution model with linear elimination and first-order absorption. Overall, nemolizumab systemic exposure

increased in a dose-dependent manner in the dose range of 0.03 to 3 mg/kg. The only observed difference was a 23 to 26% reduced exposure in AD patients compared with healthy subjects. Owing to its low immunogenicity potential, there are no safety concerns associated with nemolizumab that will preclude investigation in healthy subjects. In addition, the type of disease does not have any effect on nemolizumab PK, as similar systemic exposure and similar PK profiles were observed in subjects with AD (Phase 2 study CIM003JG) and in subjects with PN (Phase 2 study SPR.115828) when treated with the same dose of 0.5 mg/kg.

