# 11.3 Measures to Minimize Bias: Study Treatment Assignment and Blinding

# 11.3.1 Method of Study Treatment Assignment

Upon confirmation of eligibility for a subject to participate in the study, a unique randomization number will be assigned to that subject manually at the baseline visit.

Approximately 192 subjects will be randomized 1:1 to receive 60 mg nemolizumab delivered with either AI or DCS. Subjects will be further randomized 1:1:1 to receive injection in 1 of 3 injection sites, i.e., abdomen, front upper thigh, or outer upper arm. Approximately 32 subjects in each delivery group will be assigned to each injection site.

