## PHARMACOKINETIC ANALYSIS

#### 16 PHARMACOKINETIC PARAMETERS

PK parameters will be calculated by a dedicated CRO with a non-compartmental analysis (NCA) using actual sampling times. For PK calculations, the program package Phoenix WinNonlin (Version 8.1 or above) will be used. Phoenix WinNonlin will also be used to generate concentration-time plots. Details related to the calculation of PK parameters will be described in a PK plan, which will be finalized before the beginning of PK analysis.

The following PK parameters will be calculated:

Primary PK parameters

Observed maximum serum concentration  $C_{max}$ 

AUC0-inf Area under the concentration-time curve extrapolated to infinity, calculated, if

feasible, as  $AUC_{0-last} + C_{last}/\lambda_z$ , where  $C_{last}$  is the last measurable drug concentration

Secondary PK parameters

Area under the concentration-time curve over the specified interval, calculated with AUC0-4 weeks

the linear trapezoidal method

Area under the concentration-time curve from administration to the last observed  $AUC_{0-last}$ 

concentration time t, calculated with the linear trapezoidal method

Time to achieve Cmax  $T_{max}$ 

Half-life, calculated, if feasible, as  $\ln 2/\lambda_z$  $t_{1/2}$ 

Total body clearance for extravascular administration, calculated, if feasible, as Cl/F

dose/AUC0-inf

Vd/F Apparent volume of distribution for extravascular administration, calculated, if

feasible, as dose/AUC0-inf •  $\lambda_z$ 

For parameters requiring the terminal elimination rate constant  $\lambda_z$  to be estimated, it will be calculated, if feasible, by log-linear regression using at least 3 concentration-time points excluding  $C_{\text{max}}$ .

All individual concentration data and PK parameters will be listed for AI and DCS together with summary statistics of geometric mean, median, arithmetic mean, standard deviation, CV, and minimum and maximum. Plots will be provided in original scale and semi-logarithmic scale for each subject in addition to mean data plots.

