# 17.1 Determination of Sample Size

From previous studies conducted with nemolizumab, inter-subject standard deviation is expected to be approximately 38.5%, which provides an inter-subject variability CV for the primary PK parameters of 40%. A sample size of 96 subjects per arm (AI or DCS) should provide a 90% power of claiming the bioequivalence between AI and DCS administration within the range 80.00 to 125.00% for the primary PK parameters with the expected GMR of 0.95.

Approximately 192 healthy subjects are planned to be randomized in this study.

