# 17.3.2 Secondary Pharmacokinetic Endpoints

Tmax will be analyzed using the non-parametric Wilcoxon signed-rank test.

 $AUC_{0-last}$ ,  $AUC_{0-4 \text{ weeks}}$ , and  $t_{1/2}$  will be analyzed using the methods applied for the primary PK parameters.

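### The primary model includes a random subject effect that one record per subject cannot separate from residual error; a fixed-effects linear model should be stated instead

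*Protocol*

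**What the plan says.** Section 17.3.1 of the protocol names a linear mixed-effects model for log AUC0-inf and log Cmax, "with treatment (administration with AI or DCS) and injection site as fixed effects and subject as a random effect". Bioequivalence is accepted if the 90% CI for the AI/DCS geometric mean ratio from this model lies within 80.00 to 125.00%. Section 17.3.2 extends the model to AUC0-last, AUC0-4 weeks and t1/2, which "will be analyzed using the methods applied for the primary PK parameters".

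The design sections describe independent groups. Section 9.1: "This is a randomized, multicenter, open-label, single-dose, parallel-group study in healthy adult subjects aged 18 to 65 years". Section 9.2 gives the reason: "The parallel-group design of this study is considered necessary due to the long terminal half-life of nemolizumab". Section 11.3.1: "Approximately 192 subjects will be randomized 1:1 to receive 60 mg nemolizumab delivered with either AI or DCS", with a further 1:1:1 randomization to one of three injection sites. Section 9.1 puts both 30-mg injections at the same location on the same side, so together they form one dose. Section 16 fixes the response variable: "PK parameters will be calculated by a dedicated CRO with a non-compartmental analysis (NCA) using actual sampling times". That yields one Cmax and one AUC0-inf per subject. The 21 concentrations behind them are not the response in this model.

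**The concern.** A random subject effect has meaning when a subject supplies more than one record, as in a crossover or replicate design. The protocol describes no second period, replicate or second device. Each subject therefore has one value per parameter, and the term for the subject and the term for residual error describe the same deviation.

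At stake is the statement of the decisive analysis. The acceptance criterion is read from this model's 90% CI, which needs a variance estimate with defined degrees of freedom. A model with a redundant variance term leaves those degrees of freedom to the program and its options, when the protocol could fix them.

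**Working it through.** **Inputs.** One record per subject and parameter (Sections 9.1, 11.3.1, 16). N = 192, 96 per arm, about 32 per device-by-site cell (Sections 9.1, 11.3.1, 17.1). Inter-subject SD 38.5%, CV 40%, expected ratio 0.95, power 90% (Section 17.1). 90% CI within 80.00 to 125.00%, that is, two one-sided tests at 5% each (Section 17.3.1).

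**1. The plan's own figures.**
- CV = √(exp(0.385²) − 1) = 0.3997, which agrees with 40%.
- SE of the log ratio = 0.385 × √(2/96) = 0.0556.
- Power of the two one-sided t-tests, integrated over the chi-square distribution of the residual variance, is 92.4% with 188 df. With 190 df (injection site left out) it is also 92.4%. The smallest size reaching 90% is 88 per arm. The stated 90% is met with some margin.

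**2. What can be estimated.** Write the model as y_i = x_i′β + u_i + e_i, with u_i the subject effect and e_i the residual. With one record per subject,

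Var(y) = (σ²_subject + σ²_residual) × I.

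- X holds the intercept, one device column and two injection-site columns, so rank X = 4. Z is the 192 × 192 identity matrix, so rank[X Z] = 192 = N.
- All four entries of the REML information matrix for the two variances equal 0.5 × 188 / 0.385⁴ = 4278.4. Its determinant is 0, so the split of the variance is not identifiable.
- In one simulated data set of 192 subjects, the REML log-likelihood was 94.8756 whether 0%, 25%, 50%, 75% or 99% of the variance was assigned to subject. The treatment estimate (−0.0507) and its SE (0.0506) were the same at every split and equal to ordinary least squares.

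The contrast and the total variance are therefore well determined. Only the split is not.

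**3. Degrees of freedom.**
- Fixed-effects model: N − rank X = 192 − 4 = 188.
- Stated model under the N − rank[X Z] rule: 192 − 192 = 0.

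**4. Consequence for the CI at the planning values** (observed ratio 0.95, SE 0.0556).
- 188 df, t = 1.653: exp(ln 0.95 ± 1.653 × 0.0556) = 86.7% to 104.1%.
- 2 df, t = 2.920: 80.8% to 111.7%, still inside the limits.
- The lower limit reaches 80% only when t = ln(0.95/0.80) / 0.0556 = 3.09.
- 0 df: no t interval is defined.

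The interval thus depends on how the degrees of freedom are counted, but at the planning values only a very small count would change the decision.

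**The case against.** The strongest reply is that nothing of substance is lost. With one record per subject, the stated model implies the same distribution for the data as the fixed-effects model. The ratio, the total variance, the power and a correctly computed CI are all recoverable. That is right, and it limits the point to a minor one.

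A second reply is that Section 17 leaves methodology to the SAP and lets the SAP supersede the protocol. The choice of degrees-of-freedom method would indeed belong there. But the protocol does not leave the model open: it states a specific one that does not suit the design. Whether that wording reaches the analysis is unknown, because the SAP is not at hand.

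Three stronger readings are tempting, and the documents support none of them.
- A reader might infer that the sample size was calculated for a different model, since Section 17.1 uses one SD with no split. That SD is the sum of the two components, so the sizing fits both models equally.
- A reader might infer biased estimates or lost power. Steps 1 and 2 of the working show neither.
- A reader who fits the model in a general package might see an SE that is too small and expect a falsely narrow CI. In the simulated data set above, one program other than SAS printed 0.039 instead of 0.0506. Its fitted variances, 0.061 and 0.0615, sum to about 0.1225, and √(0.1225 × 2/96) = 0.0505, which agrees with least squares up to rounding. The fault lies in that program's printed SE when its Hessian is singular. The protocol plans SAS, and no SAS run was made.

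**Conclusion.** The primary model is wrongly specified for a single-dose parallel-group trial: the random subject effect cannot be separated from residual error. The severity is minor. The treatment contrast, total variance, sample size and stated power are unaffected. What is affected is the definition of the decisive 90% CI. Taken literally, the model has a singular variance structure and no residual degrees of freedom under one standard counting rule, so the interval depends on how the software handles it.

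The confounding follows from the design and needs no numerical assumption. The 188 df assumes that all 192 subjects are evaluable and that no covariate is added. Section 16 calculates AUC0-inf only where feasible and Section 17.2 requires evaluable data, so the actual number may be lower. The CI figures assume the planning SD and an observed ratio of 0.95.

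**What to change.** In Section 17.3.1, remove the mixed-effects label and the random subject term. Suggested text: *Each log-transformed parameter will be analysed with a linear model (ANOVA/ANCOVA) with treatment and injection site as fixed effects. The 90% CI for the geometric mean ratio will be based on the residual mean square and its degrees of freedom.* Leave the sentence on baseline characteristics as it is; it raises a separate question. Apply the same correction to AUC0-last, AUC0-4 weeks and t1/2 in Section 17.3.2, and carry it into the SAP.

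The cost is a change of wording. Design, sample size, endpoints, acceptance limits and data collection stay the same.

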# **SYNOPSIS**

Title of Study:	A Randomized, Single-Dose, Open-Label, Parallel-Group Study in Healthy Volunteers to Assess the Relative Bioavailability of a Subcutaneous Dose of Nemolizumab When Administered with Auto-Injector Compared to Dual-Chamber Syringe
Protocol Number:	RD.06.SPR.201590
Investigators/Stud y Sites:	Approximately 3 study sites are planned in the United States
Phase of Development:	Phase 1
Objectives:	The primary objective is to compare the rate and extent of absorption a single dose of nemolizumab administered with auto-injectors (AI; test) versus dual-chamber syringes (DCS; reference) under controlled conditions in healthy adult subjects.
	The secondary objectives are to assess the safety and immunogenicity of nemolizumab following administration with AI or DCS in healthy adult subjects.
Study Endpoints:	Primary Endpoints:
	Change of primary pharmacokinetic (PK) parameters: C max (rate of absorption) and AUC 0-inf (extent of absorption) of nemolizumab administered with AI or DCS
	Secondary Endpoints:
	Change of secondary PK parameters (AUC 0-4 weeks AUC 0-last , T max , and t 1/2 ) of nemolizumab administered with AI or DCS
	Assessment of the immunogenicity (anti-drug antibodies, ADA) of nemolizumab administered with AI or DCS
	• CCI
Study Design:	This is a randomized, multicenter, open-label, single-dose, parallel-group study in healthy adult subjects aged 18 to 65 years to assess the relative bioavailability of a 60-mg subcutaneous dose of nemolizumab administered with AI compared to DCS, stratified by injection site. The 60-mg dose will be administered as 2 successive subcutaneous injections of 30 mg (AI or DCS).
	The study duration will be up to 16 weeks and consists of an up to 28-day screening period and a 12-week PK evaluation period.
	The screening period will evaluate subject eligibility. At baseline, approximately 192 subjects will be randomized 1:1 to receive 60 mg nemolizumab delivered with either AI or DCS. Subjects will be further randomized 1:1:1 to receive injection in 1 of 3 injection sites, i.e., abdomen, front upper thigh, or outer upper arm. Approximately 32 subjects in each delivery group will be assigned to each injection site.

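### The primary model leaves out study centre in a trial run at about 3 centres; adding it is a small, nearly free gain in precision, not a repair of bias

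*Protocol*

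**What the plan says.** Section 9.1 describes the design: "This is a randomized, multicenter, open-label, single-dose, parallel-group study". The Synopsis gives the number of centres: "Approximately 3 study sites are planned in the United States".

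On allocation, Section 11.3.1 states that "a unique randomization number will be assigned to that subject manually at the baseline visit" and that "Approximately 192 subjects will be randomized 1:1 to receive 60 mg nemolizumab delivered with either AI or DCS", followed by a 1:1:1 split over abdomen, thigh and arm. The only stratification named is in Section 9.1: "administered with AI compared to DCS, stratified by injection site". That is the body location, not the centre. The protocol does not say whether the list is balanced by centre.

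Section 11.5.2 makes clear that centre staff give the injections.

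The primary model in Section 17.3.1 is a linear mixed model on the log scale, "with treatment (administration with AI or DCS) and injection site as fixed effects and subject as a random effect". It then adds: "Some clinically important baseline characteristics may also be included in the model". Those characteristics are not named. Section 17.3.2 applies the same method to AUC0-last, AUC0-4 weeks and t1/2. Section 17 says that the SAP supersedes the protocol where the two differ.

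**The concern.** Centre is known at randomisation and could plausibly carry differences in exposure, for example through the body size of the subjects recruited or through how staff prepare and give the injection. Section 7.2 says the study addresses delivery differences between the devices such as injection depth, angle and time, so handling at the centre is not remote from what is being measured.

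The random subject effect does not absorb this. Each subject receives one dose and gives one value per parameter, so subject variance cannot be separated from the residual. Between-centre variance therefore sits in the error term.

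The comparison is entirely between subjects, with a planned CV of 40%. Any explainable variance left in the error widens the 90% CI that has to fit within 80.00 to 125.00%. What is at stake is precision, and so the chance of concluding bioequivalence when it is true.

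**Working it through.** **Inputs from the protocol.** 96 subjects per arm, log SD 0.385, CV 40%, GMR 0.95, limits 80.00 to 125.00% and stated power 90% (Section 17.1); a 90% CI, i.e. two one-sided tests at 5% (Section 17.3.1); about 3 centres (Synopsis).

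**Input not in the protocol.** The share v of log variance explained by centre. I assume 0 to 20% and show the range.

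**1. The plan's own figure.**
- Log SD: √ln(1 + 0.40²) = 0.385, as stated.
- SE of the log ratio: 0.385 × √(2/96) = 0.0556.
- Lower limit: (ln 0.95 − ln 0.80)/0.0556 − 1.645 = 3.093 − 1.645 = 1.448, so Φ = 0.926.
- Upper limit: (ln 1.25 − ln 0.95)/0.0556 − 1.645 = 4.938 − 1.645 = 3.293, so Φ = 0.9995.
- Power by normal approximation: 0.926 + 0.9995 − 1 ≈ 92.6%. Integrating over the distribution of the estimated variance gives 92.4%.

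This is a little above the stated 90%. Entering 0.40 directly as the log SD gives 90.6%, which matches it. Either way, the claim of 90% is met without a centre term.

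**2. Adding centre, total log SD held at 0.385.** The residual SD becomes 0.385 × √(1 − v). Residual degrees of freedom fall from 192 − 4 = 188 to 186.

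| Centre share v (assumed) | Residual SD | SE of log ratio | Power, no centre term | Power, centre as fixed effect |
|---|---|---|---|---|
| 0% | 0.385 | 0.0556 | 92.4% | 92.4% |
| 2% | 0.381 | 0.0550 | 92.4% | 92.8% |
| 5% | 0.375 | 0.0542 | 92.4% | 93.5% |
| 10% | 0.365 | 0.0527 | 92.4% | 94.5% |
| 20% | 0.344 | 0.0497 | 92.4% | 96.4% |

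The table treats device as balanced within centres. Simulation with allocation not balanced by centre (3 centres of 64, 12,000 runs per setting) shows what chance imbalance costs the adjusted model. At v = 0 the mean SE is 0.0558 with centre and 0.0555 without, and power is 92.3% against 92.5%, a difference within simulation error.

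**3. If centre variance comes on top of 0.385.** The total SD is then 0.385/√(1 − v). Power without the centre term is 91.2%, 89.8% and 86.4% at v = 5, 10 and 20%; with it, power returns to about 92.4%. The protocol does not say whether the SD taken from previous studies already contains centre variation.

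**4. Is the ratio biased or the test invalid?** In the same simulations without a centre term, the mean estimated GMR is 0.949 to 0.951 for a true 0.95. The false-acceptance rate at a true 0.80 is 4.7 to 5.0%. The model SE (about 0.0555) agrees with the empirical SD of the estimate (0.055 to 0.056). So there is no bias and no inflated error.

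**The case against.** The strongest reply is that nothing here is wrong. Randomisation protects the ratio, and the unadjusted SE already includes the centre variance and the effect of chance imbalance. The planning SD may already contain centre variation. The protocol leaves room for covariates, and a SAP that is not shown here may add centre.

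Most of this stands, and it limits the point to precision. It does not remove it. Section 17.3.1 sets out a concrete model without centre, and a design factor such as centre does not clearly fall under optional baseline characteristics.

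Three stronger readings are tempting, and the protocol does not support them:

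- **Allocation is unbalanced by centre.** Section 11.3.1 is silent on this. Numbers issued manually are compatible with lists blocked within each centre.
- **Manual, open-label issue makes imbalance more likely.** Handing out numbers from a prepared list does not change the balance of that list. If staff did subvert allocation, a centre term would not repair it.
- **A chance imbalance seriously lowers power.** Suppose one of three equal centres has 15% higher exposure and there is no balancing by centre. The AI count in that centre of 64 has SD √(64 × 0.25 × 128/191) = 3.27. An imbalance of 1.96 SD shifts the log ratio by 1.96 × 2 × 3.27/96 × ln 1.15 = 0.0187. A true 0.95 then behaves like 0.932 (power 86.4%) or, just as likely, like 0.968 (96.0%). Quoting only the adverse tail misleads. In that scenario centre explains (2/9)(ln 1.15)²/0.385² = 2.9% of the variance, and adjusting raises power from 92.4% to 93.0%.

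Nor would a centre main effect remove a device difference that itself varies between centres.

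**Conclusion.** The point holds as a minor improvement. The primary model omits a known design factor. Under randomisation the AI/DCS ratio stays unbiased and the 90% CI keeps its error rate, so the only cost is precision.

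If the planned SD of 0.385 already includes centre variation, the gain from adjusting is about 0.4, 1.1 or 2.1 percentage points of power per parameter at centre shares of 2, 5 or 10%. It is practically nil if centre explains nothing. These shares are assumptions. Only if centre variance came on top of 0.385 and reached about 10% would power without the term fall just below the stated 90% (89.8%), and the protocol gives no sign either way.

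**What to change.** In Section 17.3.1, name study centre as a prespecified fixed effect, alongside device and body injection site, in the models for AUC0-inf and Cmax. Carry the same term into the secondary parameters that Section 17.3.2 analyses by the same method (AUC0-last, AUC0-4 weeks and t1/2). If centre is to be left out, give the reason before data are available.

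With 3 centres this costs two residual degrees of freedom, from 188 to 186, which leaves power at 92.4% when there is no centre variance. No extra subjects, samples or procedures are needed.

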### 7.5 **Dose Selection Rationale**

In this study, subjects will receive a 60-mg dose of nemolizumab via 2 subcutaneous injections of 30 mg nemolizumab. The proposed dose corresponds to the loading dose for both DCS and AI presentations and represents the highest strength used in Phase 3 clinical studies with nemolizumab. The extrapolation of the 60-mg dose to the 30-mg dose will be supported by the population PK model built with data collected in previous clinical studies with nemolizumab.

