## 14.4 Height and Weight

Height and weight will be measured, according to Section 12.1.

Subjects must weigh at least 45 kg and have a body mass index between  $\geq 18.0$  and < 30.0 kg/m^2 at both screening and baseline visits to be enrolled into this study.

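### The primary model leaves baseline covariates optional and unnamed; naming log body weight would gain precision at almost no cost

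*Protocol*

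**What the plan says.** Section 17.3.1 sets out a linear mixed-effect model for log-transformed AUC0-inf and Cmax. Treatment and injection site are fixed effects and subject is a random effect. It then adds: "Some clinically important baseline characteristics may also be included in the model". No characteristic, functional form or inclusion rule is given there or elsewhere in the protocol. The result of this model decides the trial: "Acceptance criterion for bioequivalence is a 90% CI for the test/reference ratio of the geometric means", to lie within 80.00 to 125.00%.

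Three other places bear on the point:

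- **Dose, Section 7.5:** "In this study, subjects will receive a 60-mg dose of nemolizumab via 2 subcutaneous injections of 30 mg nemolizumab". The dose is not scaled to weight.
- **Weight, Section 14.4:** "Subjects must weigh at least 45 kg and have a body mass index between" 18.0 and 30.0 kg/m², at both screening and baseline. Weight is therefore available for every randomized subject.
- **Sample size, Section 17.1:** "inter-subject standard deviation is expected to be approximately 38.5" per cent; "A sample size of 96 subjects per arm (AI or DCS) should provide a 90% power" "for the primary PK parameters with the expected GMR of 0.95". Covariate adjustment is not mentioned.

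Section 17 says that an SAP will follow protocol approval and will override the protocol where the two differ.

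**The concern.** Section 9.2 explains that the long half-life requires a parallel-group design. Each subject is therefore not his or her own control, and the whole between-subject variance goes into the CI for the geometric mean ratio. At a flat dose, body size is the obvious baseline source of such variance. The eligibility limits leave room for it: at one height, the BMI limits alone allow weight to differ by a factor of 30/18 = 1.67, and differences in height add to that.

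The protocol leaves use of this information to an unspecified choice. If weight predicts exposure, omitting it gives a wider pass/fail interval than the same data could support. If it does not, including it costs almost nothing. The stake is precision in the deciding interval. The unadjusted comparison is not biased.

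**Working it through.** **Inputs from the protocol.** Log-scale SD 0.385, 96 subjects per arm, GMR 0.95 (Section 17.1); limits 80.00 to 125.00% and 90% CI, that is two one-sided 5% tests (Section 17.3.1). The SD agrees with the stated CV: √ln(1 + 0.40²) = 0.385.

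**Assumptions, not in the protocol.** The slope of log exposure on log weight is 0.5 to 1.0 in absolute size. The SD of log weight among enrolled subjects is 0.15 to 0.20. The mid-range case is 0.75 and 0.175.

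**Step 1, the plan's own figure.** The unadjusted standard error is 0.385 × √(2/96) = 0.0556. With treatment and three injection sites in the model, the residual df are 192 − 4 = 188 and the critical t is 1.653, so the log half-width is 0.0919. Exact power for the two one-sided tests, integrating over the residual variance, is 92.4% per parameter. The stated 90% is therefore met.

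**Step 2, variance explained by weight.** R² = (slope × SD of log weight)² / 0.385².

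- Low: (0.5 × 0.15)² / 0.385² = 0.038
- Mid: (0.75 × 0.175)² / 0.385² = 0.116
- High: (1.0 × 0.20)² / 0.385² = 0.270

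**Step 3, adjusted standard error.** SE = 0.385 × √(1 − R²) × √(2/96) × √(1 + 1/186), with 187 df. The last factor allows for chance imbalance of weight between arms. The equivalent number per arm is 96 / (1 − R²).

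| Case | R² | Log half-width | Change in CI width | Power per parameter | Equivalent n per arm |
|---|---|---|---|---|---|
| Unadjusted | – | 0.0919 | – | 92.4% | 96 |
| Weight has no effect | 0 | 0.0921 | +0.3% | 92.3% | 96 |
| Low | 0.038 | 0.0903 | −1.6% | 93.1% | 100 |
| Mid | 0.116 | 0.0866 | −5.7% | 94.8% | 109 |
| High | 0.270 | 0.0787 | −14.3% | 97.4% | 131 |

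**Step 4, what the CI looks like.** At an observed ratio of 95%, the unadjusted interval is 0.95 × exp(±0.0919) = 86.7% to 104.1%. In the mid case it is 0.95 × exp(±0.0866) = 87.1% to 103.6%.

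**Step 5, break-even.** Adjustment pays once √(1 − R²) × √(1 + 1/186) falls below 1, that is R² above about 0.0054. The slope needed is √0.0054 × 0.385 / SD of log weight: 0.19 at SD 0.15 and 0.14 at SD 0.20, both well below the assumed range.

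**The case against.** The strongest objection is that naming covariates is ordinary SAP content. Section 17 defers methodology to the SAP, and the unseen SAP may already name weight. The core model, the log scale and the acceptance range are all fixed in the protocol. That limits the point: nothing required is missing from the protocol. What remains is that the protocol does address covariates in its primary model and settles the matter only with an open option, where a definite and better choice was available.

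The second objection is that the size of the gain is not in the protocol. This stands. No passage relates weight to exposure. The 38.5% SD comes from earlier studies, and Section 7.1 shows that the programme used both weight-based and flat doses, so the share of that SD due to weight at a flat dose is unknown. The lower end of the assumed range is not a floor: an SD of log weight of 0.12 with slope 0.5 gives R² of about 2% and roughly half a point of power. The 1.67 ratio compares eligibility extremes and is not the spread of enrolled weights.

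The third objection is that little turns on it: power already exceeds the target, and both intervals in Step 4 lie well inside the acceptance range. That is fair, and it is why this is a recommended improvement and not a necessary correction. Power has less to spare if subjects are lost. The protocol states no dropout allowance, and Section 10.4 says treated subjects are not replaced. If 86 per arm were evaluable (an assumption), unadjusted power would be 89.7%, against 92.5% with the mid-range weight effect.

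**Conclusion.** The point holds as an available improvement. Section 17.3.1 leaves unnamed covariates optional in the model that decides bioequivalence, although a plausible predictor is measured in everyone at no extra cost. Under the stated assumptions, adjusting for log weight narrows the 90% CI by about 2% to 14%, which is worth 4 to 35 additional subjects per arm (13 in the mid case). The downside if weight is irrelevant is about 0.1 point of power. The direction of this trade is robust, because break-even needs R² of only about 0.5%. The size of the gain is uncertain, because both the slope and the weight spread are assumed. No error or bias in the unadjusted analysis is claimed, and the stated power stands without the change.

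**What to change.** Replace the optional sentence in Section 17.3.1 with wording such as: *Log baseline body weight will be included as a covariate in the primary model for AUC0-inf and Cmax. Any further covariate will be named in the SAP, which will be finalized before any concentration data are available. The model without weight will be reported as a sensitivity analysis.*

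The same wording should be carried into the SAP. The cost is one sentence and one of 188 residual degrees of freedom. No new measurement, visit or subject is needed, and the sample size can stay as it is.
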